### Final outcome

- Recovered/ resolved - The subject has fully recovered, or by medical or surgical treatment the condition has returned to the level observed at the first trial-related activity after the subject signed the informed consent
- Recovering/resolving - The condition is improving and the subject is expected to recover from the event. This term is only applicable if the subject has completed the trial or has died from another AE.
- Recovered/ resolved with sequelae - The subject has recovered from the condition, but with lasting effect due to a disease, injury, treatment or procedure. If a sequela meets an SAE criterion, the AE must be reported as SAE.
- Not recovered/not resolved - The condition of the subject has not improved and the symptoms are unchanged, or the outcome is not known.
- Fatal - This term is only applicable if the subject died from a condition related to the reported AE.
- Unknown - This term is only applicable if the subject is lost to follow-up

### **Reporting SAE**

- Information about all SAE will be documented in the AE form and reported to Coordinating Investigator of the study, [name] [name] at [[contact]](mailto:[contact]) and UKM ethics directly within 24 hours.

### **Treatment and follow up of AE**

- Treatment of any AE is at the sole discretion of the investigator who should follow up subjects with AE until the event has resolved or until the condition has stabilised. Otherwise appropriate medical care should be arranged for the patient. Abnormal tests should be repeated until they return to baseline levels or an adequate explanation of the abnormality has been found.
- Adverse events will be explored and documented at each clinic visit.

### **Safety update**

- Any safety updates will be notified to UKM ethics committee.

## Sample size

Sample size calculation was calculated using two population proportion formulae. Prior data indicate that the proportion of cure of the patients receiving lithium was 0.91 (Bogazzi et al.) and the proportion of cure of the patients receiving carbimazole was 0.57 (Kartamihardja et al.) Thus a minimum sample size of 34 samples per group to be able to reject null hypothesis with probability power of 0.9. The type 1 error probability associated with this test of the null hypothesis is 0.05. Person's Chi Square test for independence will be used to evaluate this null hypothesis. With additional of two 20% dropout rate, the sample size is 43 samples per group.

### Hypothesis (Equality)

$$H_0: p_1 = p_2$$

$$H_a: p_1 \neq p_2$$

### Formulae for Sample Size Calculations

#### **Sample size (n) :**

$$= \frac{\{Z_{1-\frac{\alpha}{2}}\sqrt{2\bar{p}(1-\bar{p})} + Z_{1-\beta}\sqrt{p_1(1-p_1) + p_2(1-p_2)}\}^2}{(p_1 - p_2)^2}$$

where  $n$  = sample size,  
 $Z$  = level of confidence,  
 $\alpha$  = alpha,  
 $\beta$  = beta,  
 $p_1$  = proportion in Group 1, and  
 $p_2$  = proportion in Group 2.

$$= \frac{\{Z_{1-\frac{0.05}{2}}\sqrt{2(0.740)(1-0.740)} + Z_{1-0.10}\sqrt{0.910(1-0.910) + 0.570(1-0.570)}\}^2}{(0.910 - 0.570)^2}$$

$$= \frac{\{1.96\sqrt{0.385} + 1.29\sqrt{0.327}\}^2}{(0.340)^2}$$

**≈ 34 samples**

### Reference:

## Study Duration and Timeline

### Stage 1:

Recruitment period is 12 months; commencing from the dates of ethics approval. There are 2 phases of this study:

- Phase 1: Patients will be followed up for 2months duration from recruitment till date of RAI.
- Phase 2: Patients will be followed up at 1, 3, and 6months post RAI therapy.

### Stage 2:

Data collection and Data Analysis will cover a period of 18months, from January 2021 till Jun 2022.

### Stage 3:

Presentation and publication will take about 6months period from March till September 2022.

The participation duration of each subject is 8months in total. (Refer to Appendix 2)

## Study Visits and Procedures

Time line	Carbimazole arm	Lithium arm
0 (recruitment)	History, physical examination including baseline eye examination for possible thyroid eye disease will be carried out. 10mls blood will be drawn for baseline TFT, RP) and LFT.	
1 week later	-	Patients will be inquired of any possible side effects. 4mls blood will be drawn for lithium level and RP
2 months later (on RAI day)	History and Physical Examination and 8mls of blood drawn for TFT, RP, LFT	History and Physical Examination and 10mls of blood drawn for TFT, RP, LFT and TDM lithium. Patients will be inquired of any possible side effects.
1 months after RAI	History and Physical Examination and 2mls of blood drawn for TFT	
3 months after RAI	History and Physical Examination and 2mls of blood drawn for TFT	
6 months after RAI	History and Physical Examination and 2mls of blood drawn for TFT	

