### Setting

Patients who are able to comply with the requirement of radioiodine therapy and consented to participate in this trial will be given appropriate counselling. These patients will be screened for inclusion and exclusion criteria. A written informed consent will be obtained and patients will then be recruited into this study.

Once recruited, history, physical examination including baseline eye examination for possible Thyroid Eye Disease (TED) will be carried out. *TED* as defined according to the presence of eye signs in categories 2–6 of the NOSPECS classification and determined clinical activity score of thyroid eye disease according to EUGOGO criteria.

Patients will be then assessed for baseline thyroid function test (TFT), renal profile (RP) and liver function test (LFT) during screening. Patients will receive either lithium carbonate 300mg once daily or carbimazole 10mg once daily, which is the current standard therapy. The necessary precautions will be given with regards to the study drugs.

Patients will be enquired of any possible side effects during the clinic visits. Lithium levels will be checked at week 1 and at the end of 2 months of initiation (refer study flow chart). If patient develops intolerable side effects or the lithium level exceeded therapeutic range, the confounding drug will be stopped and patient will be managed accordingly. The patient will subsequently be withdrawn from the study. It is important to note that the lithium dose used in this study is of low dose, hence the side effects risks anticipated would be low.

Current waiting period in PPUKM is about 2months. Patients will be on the above treatment for a duration of 2 months and carbimazole will be stopped 3 days prior to radioactive iodine treatment. RAI will be administered at a fixed dose of 15mCi in both groups. Bloods will be drawn for TFT, RP, LFT and lithium level on the RAI day. Lithium will be discontinued on day 3 post RAI. The timeline for stopping both the carbimazole and lithium are as per clinical practice guidelines. Patients will be followed up at months 1, 3 and 6 post RAI with TFT during each visit.

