#### **Detecting and documenting AE**

- Information about all AEs, whether volunteered by the patient, discovered by investigator questioning or detected through physical examination, laboratory test or other means, would be documented on the Adverse Event Form and followed up as appropriate. The AE form should be emailed to the coordinating investigator [name] [name] at [contact].

- When eliciting experiences of AE from a subject, ask a standard non-leading question like "Do you feel different in any way since starting the new treatment/the last visit?" This question will be put to the subject in his/her own language at each study visit.

- Each AE should be described by:

Nature of AE

- This should be documented in terms of a medical diagnosis(es). When this is not possible, the AE should be documented in terms of signs and/or symptoms observed by the investigator or reported by the subject.

Duration:

- Start and end dates

Assessment of causality:

The investigator should attempt to explain each AE and assess its relationship, if any, to the study treatment. Causality should be assessed using the following definitions:

- Very likely
  - The AE follows a reasonable temporal sequence from study treatment administration
  - Abates upon discontinuation of study treatment
  - Reappears on repeated exposure (re-challenge)
- Probable
  - The AE follows a reasonable temporal sequence from study treatment administration
  - Abates upon discontinuation of study treatment
  - Cannot reasonably be explained by known characteristics of the subject's clinical state
- Possible
  - The AE follows a reasonable temporal sequence from study treatment administration.
  - But could have been produced by the subject's clinical state or other mode of therapy administered to the subject
- Doubtful
  - The temporal association between study treatment and AE is such that the study treatment is not likely to have any reasonable association with the observed event
- Very unlikely
  - The AE is definitely produced by the subject's clinical state or other mode of therapy administered to the subject

The degree of certainty with which an AE is attributed to study treatment or alternative cause like natural history of disease or concomitant treatment should be guided by the following considerations:

- Time relationship between treatment and occurrence of AE
- De-challenge and re-challenge information, if applicable
- Known pharmacology of the drug

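### The visit table lists a side-effect enquiry only for the lithium arm, on RAI day as well as at week 1, so adverse events are ascertained unequally between the arms

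*Protocol*

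**What the plan says.** Three places in the protocol describe enquiry about adverse events without separating the arms. Detecting and documenting AE prescribes a standard non-leading question and says: "This question will be put to the subject in his/her own language at each study visit". Treatment and follow up of AE says: "Adverse events will be explored and documented at each clinic visit". Setting says: "Patients will be enquired of any possible side effects during the clinic visits".

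The table under Study Visits and Procedures is arm-specific. At week 1 the lithium cell reads "Patients will be inquired of any possible side effects. 4mls blood will be drawn for lithium level and RP" and the carbimazole cell is a dash. On RAI day the carbimazole cell reads "History and Physical Examination and 8mls of blood drawn for TFT, RP, LFT". The lithium cell for the same day also lists history and examination, and continues: "10mls of blood drawn for TFT, RP, LFT and TDM lithium. Patients will be inquired of any possible side effects". The rows for months 1, 3 and 6 after RAI list history, examination and a thyroid function test for both arms, with no side-effect enquiry in either.

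Study Design states that the trial is open label. Setting also makes side effects a reason for stopping: "If patient develops intolerable side effects or the lithium level exceeded therapeutic range, the confounding drug will be stopped and patient will be managed accordingly". Withdrawal from the study then follows.

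**The concern.** Adverse-event counts depend on how often and how directly patients are asked. If staff work from the visit table, lithium patients are asked at two scheduled points before or on RAI day and carbimazole patients at none. If staff follow the general rule, the count is two against one. Both patients and staff know the allocation, so blinding offers no protection against a difference in asking.

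What is at stake is the fairness of any tabulation of adverse events by arm. Background and Significance presents carbimazole's side effects as a reason why lithium is used as an alternative, and describes lithium at this dose as carrying little risk. Readers will therefore look at relative tolerability even though it is not a formal objective. Asking one arm more often would tend to make lithium look relatively worse and to under-record carbimazole events.

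**Working it through.** No figure in the protocol is in dispute here. The check sets the sections side by side and counts scheduled enquiries.

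**Step 1: scheduled contacts after recruitment, from the visit table.**

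| Contact | Lithium attends | Enquiry listed, lithium | Carbimazole attends | Enquiry listed, carbimazole |
|---|---|---|---|---|
| Week 1 | yes | yes | no | – |
| RAI day (2 months) | yes | yes | yes | no |
| Month 1 after RAI | yes | no | yes | no |
| Month 3 after RAI | yes | no | yes | no |
| Month 6 after RAI | yes | no | yes | no |

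**Step 2: enquiries about the pre-RAI treatment period.**

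- Table alone: lithium 1 + 1 = 2; carbimazole 0 + 0 = 0.
- Each-visit rule applied to the visits scheduled: lithium 1 + 1 = 2; carbimazole 0 + 1 = 1.

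The gap is 2 to 0 on the first reading and 2 to 1 on the second. Study Design stops carbimazole 3 days before RAI and lithium on day 3 after it, so the one carbimazole enquiry also falls just after that drug has ended.

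**Step 3: which differences contradict the text.**

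- *RAI day.* Both arms attend and both have history, examination and bloods. Only the lithium cell adds the enquiry. The general rule covers every visit and makes no exception by arm, so the table and the rule do not agree. The need for a lithium level explains the larger blood volume; it does not explain limiting a general symptom question to one arm.
- *Week 1.* Carbimazole has no visit, so a rule about visits is not breached. This is an unequal schedule and not a contradiction. The visit has an evident purpose, the lithium level and renal profile, but the enquiry attached to it has no counterpart in the other arm.
- *Months 1, 3 and 6.* The table omits the enquiry in both arms. This also departs from the general rule, but equally, so it creates no imbalance.

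**Step 4: number of contacts needed to equalise week 1.** The Sample size section gives 34 per group before dropout. Allowing for 20% dropout, 34 / (1 − 0.20) = 42.5, rounded up to 43, which matches the stated 43 per group. One extra call per carbimazole patient is therefore about 43 calls.

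**The case against.** The strongest reply is that the table is a summary and the adverse-event sections govern. Nothing in the protocol gives the table precedence. Because it also leaves the enquiry out at months 1, 3 and 6, where the general rule plainly applies, it clearly does not list every adverse-event procedure. History and examination on RAI day can bring out events in the carbimazole arm. This stands in part: the count of zero for carbimazole is the less plausible reading, and staff who follow the adverse-event sections would ask both arms on RAI day. It does not explain why the enquiry is written for one arm and not the other in the same row, and it leaves the two-to-one difference from week 1.

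A second reply is that no objective, hypothesis or endpoint calls for a between-arm comparison of adverse events. That is correct and limits the weight of the point. The protocol nevertheless sets up detailed adverse-event collection, and any display by arm would carry the asymmetry.

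Three stronger readings are tempting, and the documents support none of them.

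- *A quantified inflation.* If each enquiry independently detects an event with probability d, two detect 1 − (1 − d)². Assuming d = 0.4, 0.6 and 0.8 gives 0.64, 0.84 and 0.96, hence ratios of 1.6, 1.4 and 1.2 against a single enquiry. Both d and independence are assumptions, and the model fits poorly. A transient week-1 symptom may be gone at two months, and one that starts later cannot be found at week 1. The standard question also asks about change since treatment began or since the last visit, so a single RAI-day enquiry covers carbimazole's whole two months, subject to recall.
- *Unequal loss of cure data.* The wording in Setting, "If patient develops intolerable side effects or the lithium level exceeded therapeutic range", might suggest that extra asking produces extra lithium withdrawals. Side effects bad enough to be intolerable are the ones most likely to be volunteered, and the protocol records volunteered events. How many withdrawals an additional enquiry would trigger cannot be derived from the protocol.
- *Lithium chosen for low toxicity.* Background and Significance says that lithium's potential adverse effects have limited its use, and proposes it because of RAI uptake. Only the dose is described as low risk.

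**Conclusion.** The point holds as an inconsistency on RAI day plus a built-in asymmetry at week 1. On RAI day the visit table gives the side-effect enquiry to lithium only, which does not agree with the general rule. At week 1 no rule is broken, but lithium has a scheduled enquiry that carbimazole lacks. Together they leave two enquiries against one if the general rule is applied, and two against none if the table alone is followed, in an open-label trial.

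The count needs no assumption beyond the schedule as printed. The bias that results cannot be sized from the document. An effect on withdrawals or on the cure endpoint is possible but not shown, and the sample size is not affected. The correction is worth making because the sections disagree and the remedy is cheap.

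**What to change.** In the table under Study Visits and Procedures, enter the standard question from Detecting and documenting AE in both columns on RAI day. Enter it also in the month 1, 3 and 6 rows so that the table matches the adverse-event sections.

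For week 1, choose one of two options:

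1. Add a short telephone enquiry for the carbimazole arm, using the same question and with no blood taken. The cost is about 43 calls.
2. Leave the schedule as it is, and state that adverse-event frequency will be compared between arms only on enquiries common to both, with lithium week-1 events listed separately. This adds no contacts, but the between-arm comparison is slightly less complete.

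The lithium level and renal profile checks at week 1 and on RAI day stay unchanged under either option.

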## Statistical Analysis Plan

Data will be entered and analysed using SPSS version 23 with appropriate statistical tools. Normally distributed data will be presented as mean $\pm$ SD. Non-normally distributed data will be presented as median and interquartile range. For comparison of baseline characteristics between the two groups, (lithium vs carbimazole) the independent sample t-test will be used if the numerical data is normally distributed and the Mann-Whitney U-test for non-normally distributed data. Pearson's Chi-square test will be used to compare the categorical data between the two groups (lithium vs carbimazole).  $P < 0.05$  will be used to determine statistical significance; data reported as mean Standard Deviation.

## Risk and Benefit to Participants

### Risks:

Lithium has been used extensively for treatment of various medical conditions. The dose used for this study is much lower. The study procedures are all routine procedures for the disease/condition studied. There is thus minimal risk for subjects.

### Benefits:

This study may benefit you by reducing your high thyroid hormone level in your body prior to undergoing radioactive iodine therapy without compromising the outcome of the radioactive iodine treatment.

### Risk Benefit Assessment

There is minimal risk for this study as the treatment of these patients are in accordance to standards of care. Study findings shall potentially greatly improve treatment outcomes. The expected benefit outweighs the risk to the participants and thus this study should be supported. This study examines patient-outcomes and results will be beneficial for policy makers to plan and structure comprehensive care and tailor it to best suit the patients. If patient develops intolerable side effects or lithium level above therapeutic range, the confounding drug will be stopped and will be managed accordingly. The patient will be excluded from this study.

### Ethics of Study

This study will be conducted in compliance with ethical principle in the Declaration of Helsinki and Malaysian Good Clinical Practice Guidelines.

### Informed Consent

Patients shall be informed of the study during their usual clinic visits. They will be requested to contact investigators if they are interested. An appointment will be made where the patient information sheet will be provided and explained to them. If they are willing to participate, the consent forms will be signed and dated. If they need to, they are allowed to take the information sheet home to consult with their family members, and another day for getting consent arranged.

### Privacy and Confidentiality

Study subjects' personal details will be remained confidential. Study ID will be assigned to each subject and the data that are transcribed into standardized data entry forms will only contain the study ID. All data will be entered into computer that is password protected. After completion of the study, the data saved into the computer will be erased. The hardcopy and pen drive of the data will be stored in a locked cabinet of the principle investigator and maintained for a minimum of 7 years after the completion of the study. Both will then be destroyed after 7 years of storage. Subjects will not be allowed to view their personal study data, as the data will be consolidated into a database. Subjects can write to the investigators to request access to study findings.

### Conflict of Interest

The investigators declare they have no conflict of interest.

### Publication Policy

No personal information will be disclosed, and subjects will not be identified when the findings of the survey are published.

### Termination of Study

If the study needs to be terminated, participants will be informed, and follow-up visits will be arranged.

**LIST OF MEDICATIONS NOT PERMITTED DURING THIS TRIAL**

[figure not shown]
During this trial, subjects participating in this research cannot be on these medications concomitantly:

1. Selective serotonin reuptake inhibitors (SSRI)
2. Monoamine oxidase inhibitors (MAOIs)
3. Tricyclic antidepressant (TCA)
4. Anticonvulsants
5. Methyl dopa
6. Methylxanthine
7. Muscle relaxants
8. Non-steroidal anti-inflammatory drugs (NSAIDs)
9. Phenothiazines
10. Tramadol
11. Diuretics
12. Acetazolamide
13. Anticonvulsants
14. Antipsychotic

**GANTT CHART**

Year	2020			2021				2022			
	Oct	Nov	Dec	Jan	Jun	Sep	Dec	Jan	Mar	Jun	Sep
Proposal Presentation											
Ethical Submission and Approval											
Recruitment											
Data Collection											
Data Analysis											
Writing and publication											

## STUDY FLOW CHART

**ESTIMATED BUDGET PROPOSAL**

No	Description	Price per unit (RM)	Quantity	Total amount (RM)
1.	Blood test TFT TDM Lithium Renal profile Liver function test	34 4 13 16	430 86 258 172	14 620 344 3 354 2 752
2.	Radioactive Iodine	405	86	34 830
			TOTAL	55 900
